6.2 Patients highly suspected to have acute Graft versus Host Disease

Table 6-2: Study Calendar for Patients highly suspected to have acute GHVD

	Screening	Day 1			Safety Follow-Up	Disease assessment
	Day -30 to Day 1 pre-injection	Pre-injection of [¹⁸ F]F-AraG (Baseline)	Injection of [¹⁸ F]F-AraG ^a	Post-injection of [¹⁸ F]F-AraG	Day 2-7 post-scan	Upto 6 month post-scan
Inclusion/Exclusion Criteria	X					
Informed Consent	X ^d	X ^d				
Height		X				
Weight		X			X ^c	
Vital signs		X		X	X ^c	
CBC w/diff, plts		X			X ^c	
Serum chemistry ^b		X			X ^c	
IV administration of [¹⁸ F]F-AraG			X			
PET/CT scan with investigational Agent [¹⁸F]F-AraG				X ^e		
Adverse event evaluation				X	X ^g	
Follow-up for development of aGVHD symptoms/disease						X ^f

a: Investigational Agent: Dose as assigned (5 mCi); route/schedule.

b: Albumin, alkaline phosphatase, total bilirubin, bicarbonate, BUN, calcium, chloride, creatinine, glucose, LDH, phosphorus, potassium, total protein, SGOT[21], SGPT[45], sodium.

c: Obtained as part of the standard of care by the Bone Marrow and Transplant group for in-patients (for in-patients)

d: Procedure may be done during screening period or on Day 1 prior to injection of study drug.

e: Scan 1: head to toe PET/CT scan 60 minutes post injection); OPTIONAL head to toe PET/CT scan 30-minutes post-injection

f: Chart review for up to 6 months post scan to monitor disease progression.

g: Collected at one time point within the time interval (day 2 – day 7) post-scan

	Screening	Day 1			Safety Follow-Up 1	Day 11-18: 2 nd scan			Safety Follow-Up 2	Disease assessment
	Day -30 to Day 1 pre-injection	Pre-injection of [¹⁸ F]F-AraG (Baseline)	Injection of [¹⁸ F]F-AraG ^a	Post-injection of [¹⁸ F]F-AraG	Day 2-7 post 1 st scan	Pre-injection of [¹⁸ F]F-AraG (Baseline)	Injection of [¹⁸ F]F-AraG ^a	Post-injection of [¹⁸ F]F-AraG	2-7 days post 2 nd scan	Upto 6 month post-scan
Inclusion/Exclusion Criteria	X									
Informed Consent	X ^d	X ^d								
Height		X								
Weight		X			X ^c	X			X ^c	
Vital signs		X		X	X ^c	X		X	X ^c	
CBC w/diff, plts		X			X ^c	X			X ^c	
Serum chemistry ^b		X			X ^c	X			X ^c	
IV administration of [¹⁸ F]F-AraG			X					X		
PET/CT scan with investigational Agent [¹⁸F]F-AraG				X ^e				X ^e		
Adverse event evaluation				X	X ^g	X		X	X ^g	
Follow-up for development of aGVHD symptoms/ disease										X ^f

6. 3 Patients at high risk of developing acute Graft versus Host Disease

Table 6-3: Study Calendar for Patients at high risk of developing acute GHVD

a: Investigational Agent: Dose as assigned (5 mCi); route/schedule.

b: Albumin, alkaline phosphatase, total bilirubin, bicarbonate, BUN, calcium, chloride, creatinine, glucose, LDH, phosphorus, potassium, total protein, SGOT[21], SGPT[45], sodium.

c: Obtained as part of the standard of care by the Bone Marrow and Transplant group for in-patients (for in-patients)

d: Procedure may be done during screening period or on Day 1 prior to injection of study drug.

CONFIDENTIAL

- e: On Day 1: Scan 1: head to toe PET/CT scan 60 minutes post injection); OPTIONAL head to toe PET/CT scan 30-minutes post-injection;
On Day 11-18: Scan 2: head to toe PET/CT scan 60 minutes post injection); OPTIONAL head to toe PET/CT scan 30-minutes post-injection
- f: Chart review for up to 6 months post scan to monitor disease progression
- g: Collected at one time point within the time interval (day 2 – day 7) post-scan #1 and at one time point within the time interval (day 2 – day 7) post-scan #2

6 ADVERSE EVENTS AND REPORTING PROCEDURES

7.1 Potential Adverse Events

Risks associated with this Investigational Agent

[¹⁸F]F-AraG has been tested in 6 healthy human volunteers, 3 advanced bladder cancer patients (2 of whom received 2 doses each), 2 breast cancer patients, and 3 squamous cell carcinoma of the head and neck cancer patients (2 of whom received 2 doses each). Any observed side effects were mild. The only side effect that occurred in more than one volunteer/patient was positive WBC esterase in the urinalysis without accompanying urinary symptoms.

Risks associated with Investigational PET/CT Imaging

The administration of the radioactive substance will feel like a slight pinprick if given by intravenous injection. Patients who are claustrophobic may feel some anxiety while positioned in the scanner. Also, some patients find it uncomfortable to hold one position for more than a few minutes. The subjects will not feel anything related to the radioactivity of the substance in their body. The substance amount is so small that it does not affect the normal processes of the body. Procedures such as isotope injection are standard procedures currently used in the clinical PET and Nuclear Medicine clinics and the usual sterile methods will be used.

Risks from PET imaging include exposure to ionizing radiation and the placement of an intravenous line. Total time required for each PET study will be approximately 90-120 minutes. The radiation the participants will receive as a result from participating in this study includes radiation from administration of [¹⁸F]F-AraG and the accompanying CT scans for attenuation correction. This radiation exposure is for research purposes only.

- The amount of radiation dose the healthy group will receive from one of [¹⁸F]F-AraG PET/CT is 11.7-12.3 mSv (2.7mSv from 163MBq for females and 3.3 mSv from 211MBq of [¹⁸F]F-AraG for males plus a further 9mSv from the three CTs (one cardiac and two whole body CT scans) for attenuation correction acquired usually before the PET acquisitions.
- The amount of radiation dose the GVHD group will receive from one [¹⁸F]F-AraG PET/CT session is 5.7-6.3 mSv (2.7mSv from 163MBq for females and 3.3 mSv from 211MBq of [¹⁸F]F-AraG for males plus a further 3mSv from the whole body CT scans for attenuation correction. If a patient is able to withstand longer times in the scanner they will undergo a further PET acquisition at 30 minutes for which 1 more CT scans will be performed usually before the PET acquisition (and an additional 3mSv dose will be received).

This amount of radiation involves minimal risk and is necessary to obtain the research information desired. Procedures will be in place for verification of correct radiopharmaceutical dose and route of administration (i.e., each dose will be double checked for dosimetry and quality by a researcher and technologist).

Risks associated with aGVHD

Patients highly suspected to have aGVHD or who are at high risk of developing aGVHD may experience side effects from underlying disease while participating in this study. Acute GVHD is characterized by a wide spectrum of host tissue injuries in the gastrointestinal (GI) tract, liver, skin, and lungs; causing a wide range of symptoms [3, 5]. In this setting, a very large number of

Grade 1 and 2 adverse events (AEs) are expected to occur, regardless of whether or not a patient is participating in a research study. Expected AEs include a number of specific AEs that are associated with acute GVHD.

The Protocol Director (PD) or designee will assess each AE to determine whether it is unexpected according to the Informed Consent, Protocol Document, or Investigator's Brochure, and related to the investigation. Unless specifically determined otherwise by the investigator, the following events are considered expected in the early post-transplant setting.

- Alopecia
- Anemia
- Anorexia
- Bleeding, including requiring transfusions
- Cardiac arrhythmias
- Central venous catheter infections
- Constipation
- Diarrhea
- Edema
- Fatigue
- Febrile episodes
- Gastritis
- Graft failure
- Graft versus host disease
- Hematuria
- Hypertension
- Hypotension
- Hypoxia
- Incontinence
- Infections, including sepsis
- Insomnia
- Laboratory abnormalities
- Mental status changes and mood alterations
- Mucositis
- Nausea
- Neutropenia
- Pain
- Pleural effusion
- Pneumonitis
- Rash
- Seizures
- Sinusoidal obstructive syndrome
- Tachycardia
- Thrombocytopenia
- Thrombotic microangiopathy
- Tremor
- Vomiting

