1.2. Secondary Objectives

The tracer's pharmacokinetics, biodistribution, dosimetry and toxicity will also be studied in GVHD patients having been previously studied in healthy volunteers. Further, extended characterization of tracer biodistribution will be carried out in a small number of healthy subjects.

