The suitability of [¹⁸F]F-AraG for human studies has been validated in humans at the University of California San Francisco (UCSF). [¹⁸F]F-AraG PET/CT scans were performed on six healthy human volunteers and dosimetry was also calculated. [¹⁸F]F-AraG exhibited hepatobiliary and renal clearance with highest uptake in associated organs with SUV mean values (normalized to body weight) of 13.47 \pm 1.46, 20.72 \pm 5.26 and 17.27 \pm 4.19 in liver, right and left kidneys respectively at 47-77 minutes post tracer injection (Table 1). High uptake was also observed in the myocardium as seen in mice, while relatively low background was observed in the thorax and lower abdomen. No significant adverse events or blood lab changes were observed due to

tracer administration in any of the volunteers other than slightly increased urine esterase levels. Radiation dosimetry results are shown in Table 2. These findings were recently published in Cancer Research (77(11); 2893–902, 2017).

[figure not shown]

Fig. 9: Whole body PET images of $[^{18}\text{F}]\text{F-AraG}$ in a healthy human volunteer. Frontal (top panel) and dorsal (bottom panel) coronal PET images taken immediately after intra-venous injection of the tracer and at serial time points in one of the 6 humans imaged. Highest activity is observed in the liver, kidneys and bladder, associated with $[^{18}\text{F}]\text{F-AraG}$ clearance from the body. Uptake is also observed in the heart and spleen while relatively low background activity is observed in all other tissues. Similar images were obtained from the other 5 subjects.

Site	SUV-BW _{mean}	SUV-BW _{max}
Brain Tissue	0.02 ± 0.01	0.08 ± 0.02
Cervical Lymph Node	5.2 ± 1.15	7.13 ± 1.76
Heart	2.12 ± 0.72	4.72 ± 1.37
Myocardium	3.38 ± 1.19	4.72 ± 1.37
Liver	13.47 ± 1.46	16.18 ± 2.00
Kidney (right)	20.72 ± 5.26	44.47 ± 12.44
Kidney (left)	17.27 ± 4.19	41.35 ± 10.65
Bladder	8.28 ± 6.15	10.28 ± 7.66
Muscle	0.98 ± 0.44	1.42 ± 0.66

Table 1: $[^{18}\text{F}]\text{F-AraG}$ standard uptake values for key tissues- normalized to body weight (SUV-BW) at 47-77 minutes post tracer injection in six healthy human volunteers.

SUV-BW mean and max values shown. Data shown represent averages \pm standard deviation; n=6 for each site. Average of both right and left sides of subject shown for brain tissue and cervical lymph node.

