These preliminary studies in healthy human volunteers have been promising with low background in the thorax and GI tract, making it favorable for thoracic and pelvic imaging. Favorable kinetics of [¹⁸F]F-AraG in humans along with the preclinical data support its potential as a promising tracer for early detection of GVHD and warrants its further clinical evaluation in aGVHD patients. Given the paucity of PET tracers for activated T cells in the clinic this work lays the important foundation for [¹⁸F]F-AraG PET imaging in aGVHD patients and the potential to provide crucial information to aid in the detection of activated T cell dynamics during the activation phase of aGVHD.

Organs	Male	Female
Adrenals	0.046567	0.067133
Brain	0.006380	0.007407
Breasts	0.005757	0.007547
Gallbladder Wall	0.051400	0.063033
LLI Wall	0.085107	0.012150
Small Intestine	0.047033	0.073000
Stomach Wall	0.018667	0.025367
ULI Wall	0.022600	0.033067
Heart Wall	0.052533	0.096933
Kidneys	0.877000	1.133333
Liver	0.211000	0.266667
Lungs	0.027167	0.033133
Muscle	0.009190	0.012167
Ovaries		0.016967
Pancreas	0.037300	0.050200
Red Marrow	0.013600	0.016833
Osteogenic Cells	0.007390	0.010593
Skin	0.004543	0.005790
Spleen	0.093600	0.163667
Testes	0.002780	
Thymus	0.005710	0.007800
Thyroid	0.001357	0.001633
Urinary Bladder Wall	0.085800	0.088167
Uterus	0.014133	0.017500
Total Body	0.018767	0.025200
Effective Dose	0.0138 mSv/MBq	

Table 2: [¹⁸F]F-AraG human radiation dosimetry data. Mean radiation dosimetry data in 3 males and 3 females in REM/mCi. The kidneys receive the highest radiation dose followed by the liver.

For our studies at Stanford, the tracer will be administered as a single bolus injection of approximately 5 mCi into a hand or arm vein. The rationale for the starting dose is based on dosimetry studies already performed in healthy human volunteers where the dose limiting organ was found to be the kidney and the annual dose characterized as 5mCi. Please refer to the imaging protocol for recommended limits for male and female subjects. The major route of clearance based on initial clinical studies is the liver and kidney.

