13. Participants will undergo a safety follow-up at one time point within the time interval (day 2 – day 7) post-scan for blood sample collection for blood chemistry and hematology and also for observation for vital signs. For in-patients we will use the blood samples and vital signs

obtained as part of the standard of care by the Bone Marrow and Transplant group. Out-patients will have to return to the clinic for the safety follow up.

14. Adverse drug events will be recorded at one time point with the time interval of 2-7 days after [¹⁸F]F-AraG injection/scan in the case report form.
15. Patients in the high risk of developing GVHD arm will undergo the above protocol once more 10-17 days after the first scan.
16. A post safety follow up will be conducted for up to 6 months via chart review to assess progression or development of aGVHD.

Safety Follow-up [range: One time point within the interval (Day 2 to Day 7) post-scan

1. BP, HR, Temperature, Blood Oxygen %, and Respiratory Rate will be recorded.
2. Blood will be collected for CBC, and Metabolite Analysis.
3. Adverse events will be collected at one time point within the time interval (day 2 – day 7) post scan.

Healthy subjects and out-patients will need to come in to the clinic for the safety follow up. For in-patients (GVHD group)-we will obtain the blood samples and vital signs obtained as part of the standard of care by the Bone Marrow and Transplant group.

Subjects with suspected acute GVHD OR at high-risk of aGVHD will be followed for 6 months post their last scan to evaluate disease (progression/development) by chart-review.

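### The tracer's only recurrent known side effect was an asymptomatic urinalysis finding, yet no cohort has a scheduled urinalysis, so the toxicity objective does not assess it systematically

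*Combined protocol and SAP*

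**What the plan says.** **The objective.** Section 1.2 states: "The tracer's pharmacokinetics, biodistribution, dosimetry and toxicity will also be studied in GVHD patients".

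**The known signal.** Section 7.1 describes prior exposure as "6 healthy human volunteers, 3 advanced bladder cancer patients (2 of whom received 2 doses each), 2 breast cancer patients, and 3 squamous cell" carcinoma patients of the head and neck, two of whom also had two doses. It calls all observed effects mild and adds: "The only side effect that occurred in more than one volunteer/patient was positive WBC esterase in the urinalysis", with no urinary symptoms. Section 2.2, on the six healthy volunteers, reports no significant adverse events or blood laboratory changes from "tracer administration in any of the volunteers other than slightly increased urine esterase levels".

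**The safety assessments.** Section 5.1 schedules vital signs, CBC and a chemistry or metabolic panel before injection, vital signs after the scan, and vital signs and blood tests at one visit on day 2-7. On laboratory work, the Safety Follow-up list says only: "Blood will be collected for CBC, and Metabolite Analysis". For in-patients, the standard-of-care data to be used are blood samples and vital signs. The chemistry footnote to Tables 6-1 to 6-3 lists serum analytes, including BUN and creatinine. Section 9.1.1 says side effects will be evaluated from vital signs and blood laboratory data.

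**Urine.** The only urine test is one permitted form of the pregnancy test in healthy women, done before injection (Section 5.1 and Table 6-1).

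**The concern.** The plan sets out to study toxicity in a new and sicker population. It names one effect that recurred in earlier subjects, and then schedules no test that could show it. The finding had no symptoms, so asking about adverse events will not reveal it, and neither vital signs nor blood tests measure it.

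At stake is how the safety result can be read. A report that lists no urinary findings would reflect the absence of a scheduled test, and a reader could take it as evidence that positive urine esterase did not recur in GVHD patients. Arm 2 patients are injected twice, with no urine check around either injection.

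**Working it through.** The plan gives no figure on this point, so there is none to reproduce. The check has two parts: the schedule, and an illustration of size.

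**1. Schedule, place by place**

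- Section 5.1, overview for patient groups: vital signs, CBC, metabolic panel. No urinalysis.
- Section 5.1, healthy subject protocol: vital signs, chemistry, hematology, EKG leads, pregnancy test. No urinalysis.
- Section 5.1, GVHD patient protocol and Safety Follow-up: vital signs, chemistry, hematology. No urinalysis.
- Tables 6-1, 6-2 and 6-3: urinalysis rows in 0 of 3.
- Section 9.1.1: vital signs and blood laboratory data.

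The remaining route is Section 7.2. A non-serious event is logged if it is attributed to the agent or a study procedure, or if it leads to withdrawal. An incidental positive urinalysis could enter that way, but it would be unsystematic and would have no paired baseline. Section 7.1 also lists laboratory abnormalities among the events expected after transplant, which makes attribution to the tracer less likely.

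**2. Size, as an illustration**

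Inputs:

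- Prior subjects (Section 7.1): 6 + 3 + 2 + 3 = 14. Administrations: 14 + 2 + 2 = 18.
- Prior cases: not stated. The text implies at least 2. Using 14 as the denominator assumes that all 14 had a urinalysis, which the documents do not say.
- Target group: up to 25 GVHD patients (Section 10.7), because Section 1.2 states the objective for them.

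Formulas: expected cases = 25 × p; chance of at least one case if all were tested = 1 − (1 − p)^25.

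For p = 2/14 = 0.143: 25 × 0.143 = 3.6, and 1 − (12/14)^25 = 0.979. The exact 95% CI for 2/14 is 1.8% to 42.8%, which gives 25 × 0.018 = 0.45 (roughly 0.5) and 25 × 0.428 = 10.7.

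| Assumption | p | Expected in 25 | P(at least one) |
|---|---|---|---|
| Lower 95% limit for 2/14 | 1.8% | about 0.5 | 0.36 |
| 2 of 14 | 14.3% | 3.6 | 0.979 |
| 3 of 14 | 21.4% | 5.4 | 0.998 |
| 4 of 14 | 28.6% | 7.1 | >0.999 |
| 6 of 14 | 42.9% | 10.7 | >0.999 |

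Under the current schedule, the number of cases found by a protocol test is zero at any rate, because no such test is done.

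**The case against.** The strongest reply is that the scope was chosen deliberately. Section 7.2 aims to capture clinically significant events and to avoid collecting uninformative ones, and a mild, asymptomatic dipstick result may look uninformative. This stands only in part. The same section focuses collection on events useful for assessing the tracer's safety, and the single recurrent prior effect fits that description.

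Several further points stand and limit the claim:

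- **Detection.** A reader might infer that the trial cannot detect the effect. Section 7.2 does not support that, since an incidental clinical urinalysis attributed to the tracer would be logged.
- **Kidney.** A reader might link the finding to the dosimetry, where Section 2.2 notes "The kidneys receive the highest radiation dose followed by the liver", and conclude that renal safety is unmonitored. No passage connects urine esterase with kidney dose. BUN and creatinine are measured at baseline and follow-up in every cohort, and around both Arm 2 scans.
- **Cumulative effect.** A reader might expect a build-up after two injections. The documents give no evidence of one. Section 7.1 includes four patients who had two doses, and it still describes all effects as mild.
- **Transfer of the rate.** Three of the 14 prior subjects had advanced bladder cancer. Section 2.2 shows the signal in healthy volunteers too, but the count per group, the timing and the baseline values are not given.
- **Attribution.** Section 7.1 expects neutropenia, infection and hematuria after transplant, and there is no uninjected control group. A paired baseline helps but does not remove this problem.

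**Conclusion.** The point holds as a gap in assessment. The only side effect seen in more than one prior subject is not systematically assessed in any cohort, although toxicity in GVHD patients is a stated secondary objective.

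The size is uncertain. If the rate were 2/14, about 3.6 cases would be expected in 25 GVHD patients, with a range of roughly 0.5 to 10.7. This assumes the smallest count consistent with the text, a urinalysis in all 14 prior subjects, and a rate that carries over to transplant patients. The documents confirm none of the three. The conclusion about the schedule needs none of them.

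The gap does not touch the primary objective or the main analyses, and the earlier effect was mild. It should be fixed because the remedy is cheap and because the toxicity result would otherwise say nothing planned about the one known signal.

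**What to change.** - Add a urine dipstick with WBC esterase at baseline and at the existing day 2-7 safety visit in Tables 6-1, 6-2 and 6-3, for both sessions in Table 6-3. Make matching additions in Sections 5.1 and 9.1.1.
- For in-patients, use standard-of-care urinalysis where available, as the plan already does for blood samples and vital signs.
- Report change from baseline descriptively by cohort, with no formal test. The five healthy volunteers are the cleanest comparison, though five is few.
- If the sponsor prefers not to test, state the reason and say in the toxicity report that urine was not assessed.

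The cost is one calendar row and a dipstick at visits that already take place. There are two downsides. Some positive results in transplant patients will come from infection or changing white-cell counts rather than the tracer, so attribution will be limited. The day 2-7 window is also a choice of convenience, because the documents do not say when the earlier positives appeared.

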7.2 Adverse Event Collection

Adverse event collection will be focused on adverse events useful for assessment of the safety of $[^{18}\text{F}]\text{F-AraG}$. The following AE monitoring schema is intended to capture all AEs that are clinically significant and/or impactful, but minimize "not informative" AE collection. Adverse events will be graded according to CTCAE v4.0.

- All AEs, both non-serious and serious, attributed to investigational agent or study procedure will be collected and documented with causality attribution (see Section 7.2 Adverse Event Attribution) on an adverse event log (AE log).
 - An adverse event is considered serious if it fulfills one of the following criteria per 21CFR§312.32(a):
 - Results in death
 - Life-threatening (patient at risk of death at the time of the event)
 - Requires inpatient hospitalization or prolongation of existing hospitalization
 - Results in persistent or significant disability
 - Other medical events that may not be immediately life-threatening or result in death or hospitalization but may jeopardize the patient or require intervention to prevent one of the outcomes listed above

- In addition, all AEs meeting the criteria of “serious” as defined at 21CFR§312.32(a), and are Grade 3 or above, will be collected regardless of attribution; and documented on an AE log, including causality attribution.
- AEs not meeting these criteria will not be collected, except as follows. AEs resulting in subject withdrawal from the study will be collected.

All Serious Adverse Events (SAEs) will be tracked until resolution or at least 30 days after the last dose of the study treatment.

The development of acute GVHD, its date of onset and overall grade, is a key component of the primary outcome measure for patients on this trial and will be monitored by chart review. Acute GVHD will be recorded on an AE log.

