5 STUDY PROCEDURES

5.1 Imaging Protocol for Patient Groups

Each subject may have up to two imaging sessions. The procedures for each imaging session is detailed below:

Day 1 (Imaging Day)

Overview of procedures prior and post injection of [¹⁸F] F-AraG:

1. Subject will participate in an informed consent session (approximately 30 minutes) and if she/he would like to continue after being fully informed she/he will sign consent form.
2. Subject will be asked to drink several glasses of water before arriving at the nuclear medicine clinic and during the study.
3. Subject will be interviewed to obtain medical history.
4. Volunteer height and weight will be measured.
5. Baseline Heart Rate (HR), Blood Pressure (BP), Blood Oxygen %, Temperature, and Respiratory Rate will be collected at baseline (5-120 minutes prior to the injection of the tracer).
6. IV line may be placed in both arms of healthy subjects for PET tracer injection and another may be used for blood collection. The GVHD patients will have double lumen catheters which can these be used for these purposes.
7. For baseline CBC analysis- 3 ml of blood will be collected and 5 ml of blood will be collected for baseline metabolic panel analysis.
8. Subject may either be positioned on the PET/CT scanner bed or another bed in the clinic (where possible the same PET-CT system should be used especially for the healthy subjects).
9. Injection of [¹⁸F] F-AraG and post-injection procedures will follow.
10. If possible, subjects should be asked to urinate prior to the start of the PET/CT scans.
11. A bolus < 5.7 mCi of clinical grade [¹⁸F] F-AraG for male volunteers or < 4.4 mCi of clinical grade [¹⁸F]F-AraG for female volunteers will be injected through IV.
12. A CT image will be acquired with the PET images.
13. The PET scanning procedure may start at the time of tracer injection or at a later time point after tracer injection. The imaging field includes the vertex to thigh for healthy subjects and vertex to feet for GVHD patients. Up to two whole-body PET scans may be performed at various time points after injection of the tracer, not to exceed 2 hours after tracer injection.
14. Blood pressure, Temperature, Blood Oxygen saturation, Heart Rate, Respiratory Rate will be measured immediately after [¹⁸F]F-AraG PET-CT procedure.
15. A safety follow up will happen at one time point within the time interval (day 2 – day 7) post-scan.
16. All observed adverse events and subject complaints will be recorded.

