7.3 Adverse Event Reporting

Both serious and non-serious AEs will be clearly noted in source documentation and listed on study-specific Case Report Forms (CRFs). Non-serious adverse events will be reported annually to FDA via an Annual Report (IND: 123591) and to IRB via Continuing Review. SAEs Grade 3 and above, and all subsequent follow-up reports will be reported to the Stanford Cancer Institute Data and Safety Monitoring Committee (DSMC) using the study specific CRF regardless of the event’s relatedness to the investigation. Following review by the DSMC, events meeting the IRB definition of ‘Unanticipated Problem’ will be reported to the IRB using eProtocol within 10 working days of DSMC review, or within 5 working days for deaths or life-threatening experiences.

Adverse events deemed serious, unexpected (i.e. not described in the protocol, Investigator’s Brochure or informed consent documents) and related to study drug must be reported to the IND Holder (CellSight Technologies) using the FDA MedWatch form 3500a within 24 hours of knowledge of event. The IND Holder is responsible for deciding whether the event meets IND Safety Reporting criteria.

If the Principal Investigator determines an unanticipated adverse effect presents an unreasonable risk to subjects, the study will be terminated as soon as possible, but no later than 5 working days after the PI makes the determination and no later than 15 working days after first receiving notification of the effect.

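### Sections 5.1 and 7.2 give different rules for which adverse events are kept, so the adverse-event part of the toxicity objective depends on which rule staff follow and, under 7.2, on investigator attribution

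*Combined protocol and SAP*

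**What the plan says.** **Section 5.1.** Step 16 of the general imaging procedure says "All observed adverse events and subject complaints will be recorded". Despite the heading, which names patient groups, several steps in that list also address healthy subjects. The safety follow-up at the end of the section says "Adverse events will be collected at one time point within the time interval" (day 2 to day 7 after the scan). Neither statement limits events by attribution, seriousness or grade.

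**Section 7.2.** Three provisions define what is kept:

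- "All AEs, both non-serious and serious, attributed to investigational agent or study procedure will be collected and documented with causality attribution".
- Events that meet the regulatory definition of serious "and are Grade 3 or above, will be collected regardless of attribution".
- For the remainder, "AEs not meeting these criteria will not be collected, except as follows". The exception that follows is "AEs resulting in subject withdrawal from the study will be collected". Acute GVHD is separately sent to the AE log.

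The same section says that all serious AEs will be followed until they resolve or for at least 30 days after the last dose, with no grade limit. For causality it points to a part of section 7.2 on attribution. The only section 7.2 in the document is the one on collection.

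**Section 7.3.** "Both serious and non-serious AEs will be clearly noted in source documentation" and listed on the case report forms. Serious AEs of Grade 3 and above go to the Data and Safety Monitoring Committee whatever their relatedness.

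**Section 1.2.** The tracer's "dosimetry and toxicity will also be studied in GVHD patients". Section 10.7 puts these at up to 25, plus 5 healthy volunteers.

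**The concern.** Toxicity is a stated secondary objective, and section 10.7 describes this as the first use of the tracer in GVHD patients. The AE data for that objective should come from one rule that every member of staff applies in the same way.

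Under 5.1 a mild event judged unrelated is recorded. Under 7.2 it is left out. If staff differ in which section they follow, the AE listing mixes two standards. If they follow 7.2, a non-serious event enters only after someone has attributed it to the tracer or a procedure, unless it leads to withdrawal or is acute GVHD. Section 7.1 gives the relatedness judgement to the Protocol Director or a designee, and no attribution method is supplied. Section 7.1 also lists many common symptoms as expected early after transplant. Expected is not the same as unrelated, but against that background a mild tracer reaction could be attributed to the transplant and not logged.

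The non-serious events reported annually to the FDA and the IRB under section 7.3 would also depend on which rule was used.

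**Working it through.** No arithmetic applies: the plan gives no AE rate, and none is needed to establish the conflict. The check takes each event type through the two sections.

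| Event type | 5.1 (step 16 and day 2-7 follow-up) | 7.2 |
|---|---|---|
| Attributed, any seriousness or grade | kept | kept |
| Unattributed, serious, Grade 3 or above | kept | kept |
| Unattributed, serious, below Grade 3 | kept | not kept* |
| Unattributed, non-serious, any grade | kept | not kept* |

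*Unless the event leads to withdrawal or is acute GVHD.

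1. The sections agree on the first two rows and disagree on the last two. The last row includes non-serious events of Grade 3 or above.

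2. The third row is not empty by definition. Section 7.2 defines seriousness by consequences such as hospitalization and grades severity separately by CTCAE. Its requirement that an event be both serious and Grade 3 or above would be redundant if every serious event already reached Grade 3.

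3. Section 7.2 does not fit with itself on that row. It undertakes to follow all serious AEs, yet its collection rule never brings in the unattributed ones below Grade 3.

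4. Safety data that do not pass through attribution are substantial. They comprise serious events of Grade 3 or above, withdrawals caused by AEs, acute GVHD, and vital signs and blood tests before and after injection (5.1, the section 6 calendars and 9.1.1). What remains exposed is the AE listing for the last two rows.

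5. Section 7.2 gives its reason for the filter, which is to avoid gathering uninformative events. Section 7.1 supplies the background: many low-grade events are expected after transplant whether or not the patient is in a study. That background does not exist in the 5 healthy volunteers, but 7.2 does not exempt them.

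**The case against.** The strongest reply is that the two sections work at different levels: 5.1 governs what is noted in source records and 7.2 governs what goes on the AE log. Staff could then comply with both. There is some support. The healthy-subject steps send events to source documents, and the arm-specific steps speak of adverse drug events, which is closer to the attributed events of 7.2. But the protocol never states this split, and its follow-up paragraph uses the same verb, collected, without a filter. The reply shows how the text could be reconciled, not that it has been.

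A second reply is that the filter is deliberate and reasoned. That stands for non-serious events in transplant patients: focused collection is a legitimate choice and is not in itself an error.

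Three stronger readings are tempting but unsupported:

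- A reader might infer that section 7.3 records every AE. It says that serious and non-serious events are noted and listed, not that all are. It can be read as handling whatever 7.2 collects, and it repeats the Grade 3 threshold for serious events.
- A reader might infer that the whole toxicity objective rests on attribution. The captures listed in the working do not, and section 9.1.1 relies on vital signs and laboratory data to find unexpected effects.
- A reader might want a probability that a real reaction goes unlogged, or might say that an upper confidence limit is invalidated. The documents give no misattribution rate, and section 10 plans no AE rate, bound or safety test.

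**Conclusion.** The concern holds in a limited form. Sections 5.1 and 7.2 conflict on two event types: unattributed non-serious AEs, and unattributed serious AEs below Grade 3, in each case apart from withdrawal-causing events and acute GVHD. Section 7.2 is also inconsistent on serious AEs and refers to attribution guidance that is absent.

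The consequence is confined to the AE component of the toxicity objective, which section 1.2 places in the GVHD patients (up to 25). For the 5 volunteers, whose stated aims in 1.2 and 9.2 are biodistribution and kinetics, the point is one of safety capture: the reason given for filtering does not apply to them. How many events would be affected cannot be estimated from the documents.

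The conclusion assumes that the collection rule in 7.2 means what it says and that no operating procedure outside these documents sets an order of precedence. It is worth correcting before enrolment proceeds, because events left unrecorded may be hard to recover later.

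**What to change.** Reconcile 5.1, 7.2 and 7.3 to one rule, and state which events enter the toxicity summary.

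- **Healthy volunteers (5):** log all AEs from injection to the day 2-7 visit, regardless of attribution.
- **Patients, serious AEs:** log every one regardless of grade or attribution, with attribution as a recorded field. This also makes the tracking sentence in 7.2 workable.
- **Patients, non-serious AEs:** the focused rule may stay. If it does, align 5.1 with it, label the resulting summary as attributed events only, and do not read it as an all-cause AE rate.
- **Attribution:** repair the cross-reference by supplying the missing text or pointing to where the method is given.
- **If 5.1 is meant for source records and 7.2 for the log:** say so explicitly.

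The cost is a wording amendment and a few extra log entries, most of them uninformative in transplant patients. Dose, scans and sample size are untouched. If the focused rule is kept, the summary of patients' non-serious events will still depend on attribution; the label makes that visible but does not remove it.
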